3.0 Study Design

This is a double blind, parallel group, placebo controlled feasibility study (see figure 1) with an enrollment target of 60 patients (30 per arm). All subjects that meet inclusion criteria as an outpatient, following a 1 month observation, will be randomized to receive an oral prophylactic dose factor Xa inhibitor (Apixaban 2.5mg po bid) or placebo for 6 months. Subjects will return for a 30 day (+/- 5 days) follow-up visit after the End of Treatment (EOT) visit. Initial randomization will occur by computerized randomization technique by the investigational drug services (IDS) at Duke University Medical Center.

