principal investigator. Pain scores during hospitalization and for the subsequent 1 week will be recorded and used for secondary analysis of daily pain scores during crisis.

Patients who during the course of the study have laboratory findings which reveal creatinine ≥ 1.5 mg/dL AND weight ≤ 60 kg; platelets $< 100 \times 10^9/L$; or develop AST or ALT > 3 times normal, will have study drug stopped and will be terminated from the study.

Patients on hydroxyurea will be included in the study and sub-analysis will be performed to control for potential differences. All patients despite treatment with hydroxyurea will need to meet inclusion criteria of having clinically significant pain which requires > 2 acute care visits.

4.2 Data and Statistical Analysis Aim 1

We power the study to test whether there is a significantly larger reduction in pain after administration of a daily prophylactic anticoagulation dose as compared to administration of a placebo. A total of 60 patients will be randomly assigned to each drug arm. The primary endpoint is the mean pain score per patient over each of four time periods. The design has two sources of variation: the variation between the patients receiving the same drug and the variation due to the interaction of time by the patients within drug arm. It is of interest to test whether the change in the pain score over the four time periods differs between the prophylactic anticoagulation dose arm and the placebo arm. From the literature the standard deviation of the mean pain score per patient is 1.5. Assume the true mean pain scores over the four time periods for the placebo and prophylactic anticoagulation dose arms are 3.9, 3.9, 3.9, 3.9 and 3.9, 3.12, 3.12, 3.12, respectively. Then, a total of 60 patients randomized equally to each drug arm will detect the difference in the change between the two arms in the mean pain scores over time, as specified by the preceding mean pain scores, with a power of at least 0.836 for a one-sided 0.05 test. Anticipating that 20% (10 patients) may have incomplete data (less than 75% of daily pain scores recorded or missing more than one dose of study drug per week), may be lost to follow up, or may drop out; we have also found a power of at least 78.4% for 50 patients.

We expect two positive effects from prophylactic doses of apixaban on the patient reported outcomes:

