- PROs assessing fatigue, physical function, and pain impact will improve in patients administered daily prophylactic dose apixaban compared to placebo.*
- We believe that there will be a significant correlation between PROs and pain scores.*

Statistical Analysis

The primary outcome of interest is to test the effect on the mean daily pain score due to the arm by time interaction. Secondary outcome will include comparison of daily pain scores while hospitalized between treatment arms and the number of hospitalizations during each treatment period.

Impact of Daily Prophylaxis Dose Anticoagulation with a Factor Xa Inhibitor (Apixaban) in Patients with Sickle Cell Disease

[figure not shown]
All analyses will be performed using SAS version 9 or greater (SAS Institute Inc., Cary, NC). Data will be analyzed using descriptive statistics including mean and standard deviation. Comparisons are to be performed using SAS's PROC GLM with a model that accounts for all fixed and random effects in the design.

5.0 Specific Aim 2: Determine the effect of prophylactic dose anticoagulation on markers of thrombin generation during outpatient steady state as well as inpatient VOC.

As described in section 3.0, we will perform a double blind, parallel group, placebo controlled feasibility study with an enrollment target of 60 patients (30 per arm).

5.1 Study Procedures Aim 2

As described earlier (Figure 1), patients begin a 1 month observation following randomization. Patients will have blood drawn on enrollment and when they return in 1 month (+/- 5 days) to begin study drug. Subsequent blood draws performed at 2 month intervals while on study drug. Blood draws will occur between 2 and 4 hours from previous dose taken and ± 5 days regardless of hospitalization. Patients will be called monthly between in person visits to assess for AE/SAE and to reinforce the importance of medication compliance. Graded incentives may be given monthly to encourage patients to continue on study and return for follow up blood draws.

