5.2 Data and Statistical Analysis

Sample Size

The same design used in Aim 1 applies to Aim 2. We analyze the change in thrombin generation from enrollment to 2 months following initiation of study drug. We hypothesize that the anticoagulation drug will

Impact of Daily Prophylaxis Dose Anticoagulation with a Factor Xa Inhibitor (Apixaban) in Patients with Sickle Cell Disease

cause a decrease in thrombin generation from baseline to two months. From the literature the standard deviation of the D-dimer measure per patient is 500. With a total of 60 patients randomized equally to each drug sequence, and conservatively assuming no correlation between D-dimer values from baseline to 2 months on the same patient, we achieve a power of 0.863 to detect a mean D-dimer difference in the change from baseline to 2 months between the placebo and the daily prophylactic anticoagulation dose groups of 250 mg/l $\{= [(1000-750) - (1000-1000)] \text{ mg/l}\}$ for a one-sided 0.05 test.

No studies to date have evaluated the influence of anticoagulants on thrombin generation as measured by CAT, therefore sample size and expected differences are calculated based on available studies examining D-dimer.

Statistical Analysis

For our primary outcome, we will compare mean changes in thrombin generation (D-dimer, TAT and phases of CAT) for patients treated with prophylactic dose anticoagulation and placebo. Secondary outcomes will include correlation of hypercoagulable and inflammatory markers to clinical outcomes (such as pain, hospitalization, and number of acute care visits).

In addition, we expect that 50% of the patients to be hospitalized and continue their medication (placebo or drug) as assigned at randomization. For these patients, thrombin generation D-dimer measures will be collected at admission, 3 days and 5 days. Therefore, as a secondary aim, for these hospitalized patients we will analyze the difference between the placebo and drug groups in the change over time in the mean D-dimer values.

Planned Analysis of Primary Endpoint

Following the enrollment of the 60 patients, and completion of the 7 month study period for each patient, all data will be subsequently analysed with the assistance of the Duke Translational Medical Institute. [name] is our lead statistician who will continue to provide statistical support and analysis through this study.

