7.0 Study Duration

Enrollment for this study will be completed within the first 12 months (average 5 patients per month), followed by 8 months to allow completion of study by all patients.

8.0 Data and Safety Monitoring Board.

The Duke University Data and Safety Monitoring Board (DSMB) is a Committee that has been established for the purpose of monitoring clinical studies. The DSMB has multiple responsibilities including:

- Assessing risk and complexity of those clinical trials that have been submitted for review
- Determining the appropriate level of data and safety monitoring
- Reviewing the reports of all serious adverse events (SAEs) that have been experienced by participants in those active clinical trials that are being monitored by the DSMB
- Reviewing the regularly submitted (usually at least yearly) data and safety monitoring reports that are required of all active clinical trials.
- Recommending appropriate actions (closure, increased monitoring, etc.) to the Principal Investigator.

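### The Aim 2 power of 0.863 does not fit the stated design of 30 per arm with zero correlation (about 0.39), and two sample-size phrases do not describe a 30-per-arm parallel trial

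*Combined protocol and SAP*

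**What the plan says.** Section 3.0 describes a double-blind, parallel-group, placebo-controlled feasibility study "with an enrollment target of 60 patients (30 per arm"; section 5.0 repeats the design and the numbers for Aim 2.

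Section 4.2, which sizes the pain endpoint, opens differently: "A total of 60 patients will be randomly assigned to each drug arm". A few lines later the power statement refers to "a total of 60 patients randomized equally to each drug arm" and gives power of at least 0.836, one-sided 0.05. The attrition sentence then takes off 10 patients and gives 78.4% power for 50.

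Section 5.2 sizes Aim 2 on D-dimer: "With a total of 60 patients randomized equally to each drug sequence", SD 500 per patient, no correlation between the baseline and 2-month values, and a difference in change of 250. The stated power is 0.863, one-sided 0.05.

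Among the Aim 1 secondary outcomes, section 4.2 lists "the number of hospitalizations during each treatment period".

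**The concern.** Size per arm drives every power statement. One sentence gives a size per arm that differs from the design section, and another borrows the language of a crossover trial. It is then natural to ask whether either slip reached a calculation. For Aim 2 the stated power and the stated inputs do not agree.

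Section 5.2 names the comparison of mean changes in thrombin generation as a primary outcome and bases its sample size on D-dimer. If the true power is near 0.39 and not 0.86, a null D-dimer result says little about whether the drug lowers thrombin generation. Readers who rely on the stated figure would give it too much weight.

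**Working it through.** **Aim 2 inputs.** Section 5.2 gives SD 500 per measure, correlation ρ = 0, a difference in change of 250 and a one-sided 0.05 test (z = 1.645). Sections 3.0 and 5.0 give a parallel design with n = 30 per arm.

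**Formulas.** Change SD = 500 × √(2(1 − ρ)). SE = change SD × √(2/n). Power = Φ(250/SE − 1.645).

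**Reproducing 0.863.** Take n = 60 per arm and use 500 as the SD of the change. Then SE = 500 × √(2/60) = 91.29, 250/91.29 = 2.739, and Φ(2.739 − 1.645) = Φ(1.094) = 0.863. This matches to three decimals.

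**The stated design.** With ρ = 0 the change SD is 500 × √2 = 707.1. With n = 30, SE = 707.1 × √(2/30) = 182.57, 250/182.57 = 1.369, and Φ(1.369 − 1.645) = Φ(−0.276) = 0.391. A noncentral t calculation gives 0.385.

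**Alternatives side by side.**

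| Set-up | SE | Power |
|---|---|---|
| 60 per arm, change SD 500 | 91.3 | 0.863 |
| 60 patients, within-patient comparison of uncorrelated values (707.1/√60) | 91.3 | 0.863 |
| 30 per arm, ρ = 0.75 (change SD 353.6) | 91.3 | 0.863 |
| 60 per arm, ρ = 0 (change SD 707.1) | 129.1 | 0.615 |
| 30 per arm, change SD 500 (the same as ρ = 0.5) | 129.1 | 0.615 |
| 30 per arm, ρ = 0, as stated | 182.6 | 0.391 |

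The SE under the stated design is twice the SE that 0.863 needs (182.57/91.29 = 2). With 30 per arm and ρ = 0, the difference in change would therefore have to be 500, not 250, to carry power 0.863.

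**Aim 1.** Section 4.2 gives SD 1.5 and means that imply a difference in change of 3.9 − 3.12 = 0.78. It gives no within-patient correlation. Assume a contrast of the first period against the mean of the three later ones, with equal correlation ρ between periods. The contrast SD is then 1.5 × √((1 − ρ) × 4/3), and normal-approximation power is:

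| ρ (assumed) | 30 per arm | 60 per arm |
|---|---|---|
| 0 | 0.540 | 0.794 |
| 0.5 | 0.794 | 0.967 |
| 0.6 | 0.867 | 0.988 |

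Solving the noncentral t version for 0.836 gives ρ of about 0.57 at 30 per arm or about 0.13 at 60 per arm. Reducing the sample by one sixth, as the plan does from 60 to 50, then gives 0.771 and 0.772 respectively, against the stated 0.784. The two explanations fit almost equally well, so 0.836 does not show which size was used. The form of the test is also open: the arm-by-time interaction over four periods has three degrees of freedom and no one-sided version, so a one-sided test implies a single contrast that section 4.2 does not name.

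**The case against.** The strongest reply is that the size is not in doubt. The opening sentence of section 4.2 starts from a total of 60 and can be read as 60 spread over the arms. The power sentence in the same paragraph says 60 in total, attrition runs from 60 to 50, sections 3.0 and 5.0 say 30 per arm, and section 5.2 plans the analysis after the 60 patients have been enrolled. Section 7.0 allows 12 months at an "average 5 patients per month", and 12 × 5 = 60. All of this stands. A reader might infer that the trial size is wrong by a factor of two, or that 120 patients and 24 months of accrual (120/5) are in play. The documents do not support that: nothing in them plans for 120.

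A reader might also infer that 0.863 proves that 60 per arm was entered. It does not. That match also needs a change SD of 500, which conflicts with the stated zero correlation; with 60 per arm and ρ = 0, power is 0.615. A within-patient comparison in 60 patients gives the identical figure. Nor can Aim 1's 0.836 be tied to 60 per arm.

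Finally, the wording on hospitalizations per treatment period might be taken to define an outcome that cannot be formed. It is imprecise, but section 4.2 divides follow-up into four time periods, and counts by period within each arm are possible.

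What the reply does not touch is that 0.863 does not follow from the inputs printed beside it.

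**Conclusion.** The point holds in limited form. Planned enrollment is 60 in total, 30 per arm. One sentence in section 4.2 and one term in section 5.2 are worded inconsistently with that, and on their own they are close to clerical.

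The Aim 2 power is wrong as written. Under the protocol's own inputs it is about 0.39, not 0.863, a gap of about 47 percentage points. It would be 0.615 if 500 were the SD of the change. Reaching 0.863 with 30 per arm needs a correlation of 0.75, where the text says zero. These results use a two-sample comparison of changes with equal SDs and no attrition. Which calculation was actually run cannot be determined from the documents.

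Aim 1's 0.836 is unverified but not shown to be wrong. With 30 per arm it is attainable at a correlation of about 0.57, under the contrast assumed above.

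**What to change.** - **Section 4.2, opening sentence:** write that a total of 60 patients will be randomized, 30 to each drug arm.
- **Section 5.2, sample size:** replace drug sequence with drug arm (30 per arm).
- **Section 5.2, power:** restate the Aim 2 power as about 0.39 under zero correlation, or state and justify the correlation (or the SD of the change) that was used and give the matching power.
- **Section 4.2, power:** confirm that the Aim 1 run used 30 per arm in a parallel design, and state the within-patient correlation and the contrast tested.

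This takes wording changes and a re-run of two power calculations. Enrollment and procedures do not change. The real cost is a less favourable Aim 2 power figure, unless a correlation near 0.75 can be supported.

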Primary analysis of daily pain scores will be performed for patients on treatment with Apixaban and compared to patients on placebo, to determine if treatment decreases daily pain scores. In addition, we will compare changes in thrombin generation from enrollment to 2 months for patients treated with Apixaban versus placebo.

Secondary analysis will be performed to evaluate differences when patients are hospitalized and on study drug versus placebo, as well as healthcare utilization for patients treated with Apixaban.

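### The primary pain test is named as an undirected arm-by-time interaction but powered as a one-sided test, and the stated minimum power depends on a within-patient correlation the plan never gives

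*Combined protocol and SAP*

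**What the plan says.** All of the following is in section 4.2 unless noted.

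- **Primary test:** "The primary outcome of interest is to test the effect on the mean daily pain score due to the arm by time interaction". It is to be run in "PROC GLM with a model that accounts for all fixed and random effects in the design". No contrast, degrees of freedom or baseline covariate is named.
- **Aim:** directional. The study is powered to "test whether there is a significantly larger reduction in pain after administration of a daily prophylactic anticoagulation dose", compared with placebo. Section 5.2 (Planned Analysis of Primary Endpoint) repeats the direction: "to determine if treatment decreases daily pain scores".
- **Power inputs:** true means of 3.9 in all four periods on placebo, and 3.9 followed by 3.12 three times on apixaban. "From the literature the standard deviation of the mean pain score per patient is 1.5". The patient-by-time variance component is named but has no value.
- **Power claim:** 60 patients in total detect this difference "with a power of at least 0.836 for a one-sided 0.05 test".
- **Losses:** "Anticipating that 20% (10 patients) may have incomplete data", and "we have also found a power of at least 78.4% for 50 patients".
- **Arm size:** one sentence, read literally, puts 60 patients in each arm. Section 3.0, section 5.0 and a later sentence of 4.2 give 60 in total, 30 per arm.

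**The concern.** An omnibus interaction over two arms and four periods asks whether the arms differ in any time pattern, in either direction. A one-sided 0.05 level does not define such a test. The plan therefore leaves two candidate primary tests with very different power, and the choice could be made after the data are seen.

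The power claim is worded as a minimum. For any test of change within patients, power depends strongly on the correlation between a patient's period means. With one SD and no correlation, the reader cannot tell which test gives 0.836 or under what condition. The fallback figure for losses also uses the wrong number of remaining patients.

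**Working it through.** **Inputs.** From section 4.2: the period means, the SD of 1.5 and one-sided 0.05. From section 3.0: 30 per arm. Assumed here, because the available text does not say: the first period is the observation month, 1.5 is the SD of a single period mean, SDs are equal across periods, and data are complete. Correlation is varied. Let b be the correlation of baseline with each later period, p the correlation among later periods, and ρ their common value under compound symmetry.

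**Effect.** Between-arm differences are (0, 0.78, 0.78, 0.78), with mean 0.585. The centred sum of squares is 0.585² + 3 × 0.195² = 0.4563.

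**Reading A, 3-df F test at 0.05.** Noncentrality = 2 × 30 × 0.25 × 0.4563 / [2.25(1 − ρ)] = 3.042/(1 − ρ), on 3 and 174 df. At ρ = 0.5 this is 6.084.

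**Reading B, one-sided 1-df contrast** (mean of the three later periods minus the first). Variance per patient = 2.25[(1 + 2p)/3 + 1 − 2b], which is 3(1 − ρ) under compound symmetry; t on 58 df. At ρ = 0.5 the SE is √(2 × 1.5/30) = 0.316.

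**Baseline-adjusted comparison (ANCOVA), one-sided.** Variance = 2.25[(1 + 2p)/3 − b²]; t on 57 df.

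| ρ | 3-df F | Change contrast | ANCOVA |
|---|---|---|---|
| 0 | 0.27 | 0.53 | 0.96 |
| 0.3 | 0.38 | 0.66 | 0.91 |
| 0.5 | 0.51 | 0.79 | 0.92 |
| 0.7 | 0.76 | 0.93 | 0.97 |

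**Recovering the stated figures.** The contrast reaches 0.836 at ρ of about 0.57, and the F test at about 0.75. Holding each at that value:

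| Patients | Plan | Contrast | 3-df F |
|---|---|---|---|
| 60 | 0.836 | 0.836 | 0.836 |
| 50 | 0.784 | 0.771 | 0.754 |
| 48 | none given | 0.756 | 0.734 |

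The contrast fits the plan's pair better than the F test, but only with a correlation that must be supplied from outside the plan. Arm size matters too: with 60 per arm, the contrast would reach 0.836 at ρ of about 0.13.

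**Do the readings differ in practice?** In 100,000 simulated trials under the plan's means at ρ = 0.5, the contrast alone was significant in 28.0% and the F test alone in 0.9%, so they disagreed in about 29%. At ρ = 0.7 the figure is about 18%. If the F test is run at 0.10 instead, disagreement is about 19% at ρ = 0.5 and 10% at ρ = 0.7.

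**Why adjust for baseline.** The contrast variance minus the ANCOVA variance is 2.25(1 − 2b + b²) = 2.25(1 − b)², which is never negative. With equal SDs, ANCOVA is therefore at least as precise for any b and p, apart from one degree of freedom. Under compound symmetry its variance peaks at 2.25 × 4/9 = 1.0 (ρ = 1/3). The SE is then √(2/30) = 0.258 and power is 0.91 with 60 patients, or 0.845 with 48. Without compound symmetry:

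| b, p | ANCOVA, 60 / 48 | Contrast, 60 / 48 |
|---|---|---|
| 0.3, 0.7 | 0.76 / 0.68 | 0.57 / 0.49 |
| 0.5, 0.8 | 0.81 / 0.73 | 0.69 / 0.60 |
| 0.3, 0.5 | 0.835 / 0.755 | 0.61 / 0.53 |
| 0.7, 0.8 | 0.945 / 0.894 | 0.90 / 0.83 |

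**If 1.5 is the SD of a patient's mean over all four periods**, the period variance is 9/(1 + 3ρ). At ρ = 0.3 the period SD is 2.18, and ANCOVA power falls to 0.66 with 60 patients and 0.58 with 48.

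**Losses.** 0.20 × 60 = 12, leaving 48.

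**The case against.** The strongest reply is that a 1-df contrast was probably meant. Section 4.2 speaks of a difference in change, assumes means that step once and stay flat, and powers a one-sided test. The contrast also comes close to the plan's second figure (0.771 against 0.784). This is a fair reading of intent, but the analysis paragraph still names only the interaction and a GLM procedure, so nothing binds the analyst to the contrast.

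Next, 0.836 is unverified rather than wrong. That is correct: a correlation of about 0.57 gives it, and nothing in the plan makes that value implausible. Section 5.2 calls zero correlation conservative for D-dimer, but that does not carry over to pain. The objection still leaves the minimum without support.

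A change contrast is valid in a randomized trial, so ANCOVA is an improvement and not the only cure. ANCOVA power also depends on correlation and can fall below 0.836. Both points stand, and they are the reason to report a range.

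The 29% applies at ρ = 0.5 and is lower in the other settings shown. The arm-size sentence is clarified elsewhere in the plan, and the miscounted losses cost the contrast only about 1.5 points (0.771 to 0.756). The four periods may be defined in a figure that is not reproduced in the text available here. Finally, the study is called a feasibility study, but section 4.2 explicitly powers a test, so that test must be identifiable.

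**Conclusion.** The concern holds. The named primary test and the powered test do not match, and no text resolves which applies. The statement of at least 0.836 is true only above a correlation of about 0.57 for the one-sided contrast or about 0.75 for the 3-df F test. At lower values, power falls as far as 0.53 or 0.27 at zero correlation. The loss count is wrong by two patients, and the arm-size sentence conflicts with the rest of the plan. These results assume 30 per arm, 1.5 as the SD of each period mean, a pre-drug first period, complete data and, where stated, compound symmetry. The choice of primary test needs to be settled before unblinding, because it can change the trial's conclusion. The count and wording errors are minor by comparison.

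**What to change.** 1. Make the primary test the one-sided 0.05, 1-df comparison of mean pain over the three on-drug periods, apixaban minus placebo, adjusted for the observation-month mean. Keep the 3-df arm-by-time interaction as supportive.
2. Define the four periods in the text, and say whether 1.5 is the SD of one period mean or of a patient's overall mean.
3. State the assumed correlation structure and restate power for the adjusted test over a declared range, not as an unconditional minimum. For example: at least 0.91 (60 patients) and 0.845 (48) under compound symmetry, but about 0.76 and 0.68 if baseline-post correlation is 0.3 and post-post correlation is 0.7.
4. Correct the loss allowance to 12 patients with 48 remaining.
5. Correct the arm-size sentence to 60 in total, 30 per arm.

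The cost is protocol and SAP wording plus one power recalculation. No new patients, visits or data are needed, because section 4.1 already collects daily pain scores in the month before study drug. The downside is small: the omnibus test for other time patterns becomes supportive, and the adjustment uses one degree of freedom.

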2.0 Study Rationale

There is not only significant morbidity associated with patients with SCD, but also costs associated with the numerous hospitalizations. Small studies have been unable to show clear benefit of the use of low dose anticoagulation in SCD due to limited sample size or the inclusion of very specific populations. However, studies have shown a decrease in the level of elevated prothrombotic markers with anticoagulation, and one

Impact of Daily Prophylaxis Dose Anticoagulation with a Factor Xa Inhibitor (Apixaban) in Patients with Sickle Cell Disease

study using full dose anticoagulation in patients with a generally milder form of SCD (with high protective hemoglobin) showed more rapid decrease in clinical pain with use of anticoagulation, suggesting a possible benefit of such therapy. Due to the paucity of data to support therapeutic dose LMWH in the more severe forms of SCD seen in the United States, we are currently performing an inpatient study to evaluate if prophylactic dose LMWH not only reduces the known hypercoagulable state, but more importantly, has a salutary effect on clinical pain scores. This study proposal attempts to critically avoid admissions by reducing daily pain scores and pain crisis as an outpatient by use of a novel oral anticoagulant.

The development of novel anticoagulants such as oral direct factor Xa (FXa) inhibitors allows the realistic use of daily prophylactic dosing as an outpatient. Past studies as detailed earlier have been limited by attempts to use subcutaneous injections or frequent, close monitoring for acenocoumarol treatment, both which are not ideal for chronic daily use. Furthermore, the use of global assays such calibrated automated thrombography (CAT) have shown further details about thrombin generation in a population which is hypercoagulable at baseline. Our studies have revealed an increase in 'thrombin burst' and intrinsic hypercoagulability which can be monitored closely by CAT during treatment with a FXa inhibitor.

There is evidence of the potential role of anticoagulants for reduction in this hypercoagulable state, and importantly reduction in clinical pain. Studies of anticoagulation in outpatients with SCD have included the use of LMWH and acenocoumarol. Both have difficulty in administration, monitoring and ultimately compliance. The development of direct factor Xa (FXa) inhibitors which are administered orally and require minimal monitoring is ideal for chronic administration.

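### The in-hospital pain and D-dimer comparisons include only patients hospitalised after randomisation, so they are not protected by randomisation and will be biased if apixaban changes who is hospitalised

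*Combined protocol and SAP*

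**What the plan says.** Under Statistical Analysis in Section 4.2 (Aim 1), the secondary outcomes are the "comparison of daily pain scores while hospitalized between treatment arms" and "the number of hospitalizations during each treatment period". Section 4.1 gives the source of the pain data: "Pain scores during hospitalization and for the subsequent 1 week will be recorded and used for secondary analysis of daily pain scores during crisis".

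For Aim 2, Section 5.2 states "we expect that 50% of the patients to be hospitalized and continue their medication". It then plans a further, secondary analysis: "for these hospitalized patients we will analyze the difference between the placebo and drug groups in the change over time in the mean D-dimer values". Samples are taken at admission and on days 3 and 5. The end of Section 5.2 repeats that the arms will be compared when patients are in hospital.

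Section 2.0 describes the study as one that "attempts to critically avoid admissions by reducing daily pain scores and pain crisis as an outpatient". Sections 4.1, 5.1 and 6.1 place randomisation at the first visit, before the observation month and before any study drug. Section 3.0 places it after the observation month. On either reading it comes before every admission on study drug.

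No section gives an adjustment for the selection, a counterpart analysis in all randomised patients, a sensitivity analysis or a caveat on interpretation.

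**The concern.** Randomisation makes the two arms comparable as whole groups. It does not make the hospitalised part of one arm comparable with the hospitalised part of the other when treatment can influence who is hospitalised. Here that influence is part of the trial's own hypothesis, and the number of hospitalisations is itself an outcome.

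If apixaban prevents some admissions, the patients still admitted on apixaban may differ in severity from those admitted on placebo. In-hospital pain or D-dimer could then differ between arms although the drug has no effect on either once a patient is admitted. A real in-hospital effect could equally be masked. A reader of the results could not separate the two explanations, and the plan does not warn of this.

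The D-dimer analysis may be selected further. Section 5.2 describes patients who are hospitalised and continue their medication, while Sections 4.1 and 5.1 let the admitting physician decide that continuing is inappropriate. By inference, patients discharged before day 3 or day 5 also leave the analysis of change.

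**Working it through.** **1. No figure to reproduce.** The plan gives no sample size, power or error rate for the in-hospital comparisons. The calculation below is only an illustration of how selection could act on pain.

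**2. Inputs.**
- From the documents: 60 patients, 30 per arm (Section 3.0); 50% expected to be hospitalised, not split by arm (Section 5.2); SD of 1.5 for the mean pain score per patient (Section 4.2). This SD belongs to the primary daily-pain endpoint. No SD for in-hospital pain is given, so it is borrowed.
- Assumed: the share hospitalised in each arm, and the correlation r between liability to be hospitalised and in-hospital pain. The scenarios average 50%, to agree with Section 5.2.
- Assumed model: patients whose normally distributed severity exceeds a threshold are hospitalised, and the drug has no direct effect on in-hospital pain.

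**3. Formula.** For a share p hospitalised, the mean standardised severity of those admitted is λ(p) = φ(z) / p, where z is the (1 − p) quantile of the standard normal and φ its density. The spurious difference, apixaban minus placebo, is

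SD × r × [λ(p apixaban) − λ(p placebo)].

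**4. Main case, 60% placebo and 40% apixaban.** λ(0.40) = 0.966 and λ(0.60) = 0.644, a difference of 0.322. With r = 0.5: 1.5 × 0.5 × 0.322 = 0.24 points. For scale, the primary endpoint is designed around 3.9 − 3.12 = 0.78 points, and 0.24 / 0.78 = 31%. That target is for a different endpoint.

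**5. Range over the assumptions (points, apixaban minus placebo).**

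| Placebo / apixaban hospitalised | r = 0.3 | r = 0.5 | r = 0.7 |
|---|---|---|---|
| 50% / 50% | 0 | 0 | 0 |
| 55% / 45% | 0.07 | 0.12 | 0.17 |
| 60% / 40% | 0.14 | 0.24 | 0.34 |
| 70% / 30% | 0.30 | 0.50 | 0.70 |

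The first row is zero because, in this model, equal shares mean that the drug has not changed who is admitted.

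**6. Check by simulation.** In the 60% / 40%, r = 0.5 case with two million simulated patients, the difference was 0.245 among the hospitalised and about 0 among all randomised. An outcome defined for everyone removes the artefact.

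**7. Precision.** At 50% hospitalised, 0.5 × 60 = 30 patients enter, about 15 per arm. Borrowing the effect of 0.78 and the SD of 1.5, a one-sided 0.05 test would have power of about 0.41. In the 60% / 40% case the groups are 0.6 × 30 = 18 and 0.4 × 30 = 12, and the standard error is 1.5 × √(1/18 + 1/12) = 0.56. The shift of 0.24 is then 0.24 / 0.56 = about 0.4 standard errors.

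**The case against.** The strongest reply has four parts.

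- **The bias is conditional.** The documents expect 50% hospitalised without distinguishing the arms, and the 22-patient acenocoumarol cross-over study described in Section 1.0 found no decrease in hospitalisations. If apixaban leaves admissions unchanged, this selection adds no bias. This stands, and the point is worded accordingly.
- **The stakes are limited.** The comparisons are secondary, in a feasibility study, and Section 5.1 keeps inpatient samples out of the primary analysis. The modelled shift of 0.24 is small beside a standard error of 0.56. This stands too, and it makes the point an improvement and not a threat to the trial. But low precision is no reason to keep an inferential comparison that is hard to interpret.
- **Part of the remedy is already planned.** The number of hospitalisations is a secondary outcome, and Section 5.2 mentions healthcare utilisation. True, but neither is presented as the randomised counterpart of the in-hospital analyses.
- **Aim 2 expressly asks about markers during inpatient vaso-occlusive crisis.** Admission counts cannot answer that. This stands: the between-arm in-hospital estimates should be relabelled, not removed.

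Three stronger readings are tempting, and the documents support none of them. A reader might infer that the comparison is certainly biased; that requires a drug effect on hospitalisation which is hoped for but not known. A reader might infer that the bias must run against apixaban; that follows from the severity-threshold model, whereas Section 5.1 samples any inpatient hospitalisation, not only those for pain. A reader might apply the same model to D-dimer with the SD of 500 in Section 5.2; that SD describes the level, whereas the plan analyses change from admission. A stable difference in level would cancel in the change, and no SD for the in-hospital change is given.

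**Conclusion.** The concern holds in conditional form. Both in-hospital comparisons are restricted by a post-randomisation event that treatment is intended to reduce, and the plan contains no safeguard or caveat. They lack the protection of randomisation and will be biased if apixaban changes who is hospitalised.

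Size and direction cannot be determined from the documents. The figure of about 0.24 pain points depends on assumed by-arm admission rates, an assumed correlation, a borrowed SD and a single severity threshold. Over the assumed range it runs from 0 to 0.70. No figure is offered for D-dimer. Nor do the documents say that a difference would be reported as a proven drug effect; they leave the interpretation open, and that is what needs to be settled. Both primary analyses are outside this point. It is a cheap improvement.

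**What to change.** In Sections 4.2 and 5.2, base the inferential between-arm secondary comparison on outcomes defined for every randomised patient:
- mean daily pain over all days, stating that hospital days are included (the plan does not say whether in-hospital scores enter the primary mean);
- number of admissions, as already planned;
- days in hospital per patient, counted as 0 for those never admitted.

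Keep in-hospital pain and the day 1, 3 and 5 D-dimer results by arm as exploratory, descriptive estimates serving the inpatient part of Aim 2. Show beside them, by arm, the share hospitalised, the number sampled on each day, and baseline features of the hospitalised patients such as genotype, hydroxyurea use, acute care visits in the previous year, observation-month pain and enrolment D-dimer. State that differences among hospitalised patients are not to be read as randomised drug effects.

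The cost is analysis wording and a little programming. In-hospital pain is already recorded under Section 4.1. Inpatient admissions are generally serious adverse events under Section 9.1.2, with onset and duration captured under Section 9.3, which should support the hospital-day count provided that admission and discharge dates are kept. No visit, sample or treatment rule changes. The downside is that the two in-hospital comparisons lose any confirmatory standing.
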